A	05MAY2021	
Document created
 
Updates made for consistency with current revision of CLP-001, Clinical Investigational Protocol SPM-020 (The RESET-RA Study) (p. 7)Updates made for consistency with current version of CLP-003, Data Monitoring Committee Charter for SPM-020 (The RESET-RA Study) (pp. 7-8)Added subgroup analyses for subjects receiving augmented therapy (pp. 9, 18, Appendix B pp. 17, 23, 29, 35, 74-77)Generalized language pertaining to software requirements for statistical analysis (p. 10)Change in nomenclature from Open-label PTE population to Treatment to Open Label (TOL), and crossover PTE population to Control to Open Label (TOL) for accuracy (p. 10, table and listing headers and footers throughout Appendices B & C)Removed reference to collecting safety data once a subject is withdrawn from the study (p. 10)
B	29JAN2024	
Rescue language and penalty as treatment failures is removed because additional RA treatment is allowed during open-label follow-up per protocol (p. 11)Added detail on missing analytes/retests (p. 11)Clarified missing data approaches (p. 12)Descriptions of ACR components removed as the section is duplicative with CLP-004; CLP-004 is referenced (p. 13)Added detail on methods for calculating and analyzing RAMRIS scores (p. 16)Removed information on calculation of SF-36 scores and replaced with reference to the same information which is found in the SF-36 User's Manual (p. 16)Clarified information on calculation of the EQ-5D-5L score (p. 17, Appendix B, pp. 63-67)Updated description of how AEs are categorized for consistency with study protocol (p. 18, Appendix B, p. 88)Added listing of subjects receiving augmented therapy (Appendix C, p. 6)
C	15JUL2024	
Extended study duration by adding 6 visits as part of open-label, long-term follow-up after completion of Week 12 (pp. 7-8, 21)

2 LIST OF ABBREVIATIONS

Abbreviation	Expansion
ACR	American College of Rheumatology
AE	Adverse event
CARLOS	Cartilage Loss Score
CDAI	Clinical Disease Activity Index
CI	Confidence interval
CMO	Chief Medical Officer
COL	Control to Open Label
CRF	Case report form
DAS	Disease Activity Score
DMARD	Disease-modifying antirheumatic drug
DMC	Data monitoring committee
EDC	Electronic data capture
EGA	Evaluator's global assessment
EQ-5D-5L	EuroQol 5 domains 5 levels
EULAR	European League Against Rheumatism
HAQ-DI	Health Assessment Questionnaire Disability Index
hsCRP	High-sensitivity C-reactive protein
IL	Interleukin
IRB	Institutional Review Board
ITT	Intent to treat
JAKi	Janus kinase inhibitors
LDA	Low disease activity
LOCF	Last observation carried forward
MCID	Minimal clinically important difference
MedDRA	Medical Dictionary for Regulatory Activities
MRI	Magnetic resonance imaging
NRI	Non-responder imputation
NRS	Numerical rating scale

Abbreviation	Expansion
OC	Observed case
PCS	Physical component summary
PD	Protocol deviation
PMA	Premarket Approval
PT	Preferred term
PTE	Per-treatment evaluable
RA	Rheumatoid arthritis
RAMRIS	Rheumatoid Arthritis MRI Scoring System
RF	Rheumatoid factor
SADE	Serious adverse device effect
SAE	Serious adverse event
SAP	Statistical analysis plan
SAS	Statistical Analysis Software
SD	Standard deviation
SF-36	Short Form Survey with 36 items
SGA	Subject's global assessment
SJC28	Swollen joint count for 28 different joints
SOC	System organ class
SOP	Standard operating procedure
TEAE	Treatment emergent adverse event
TJC28	Tender joint count for 28 different joints
TOL	Treatment to Open Label
UADE	Unanticipated adverse device effect
USADE	Unanticipated serious adverse device effect
WHO	World Health Organization

3 INTRODUCTION

This document outlines the statistical analysis plan (SAP) for the exploratory analysis during the open-label, long-term follow-up period in the RESET-RA study conducted by SetPoint Medical under protocol SPM-020 entitled “Vagus Nerve Stimulation Using the SetPoint System for Moderate to Severe Rheumatoid Arthritis: The RESET-RA Study.” The SAP specifies the listings and tabular summaries for the exploratory data analyses to be performed using the data collected during the open-label, long-term follow-up.

Note: The primary, secondary and exploratory efficacy analyses of the randomized, sham-controlled, double-blind data through Week 12 are detailed in a separate SAP (CLP-004).

3.1 Study Objective

The overall objective of this study is to evaluate the safety and efficacy of the SetPoint System for the treatment of adult patients with active, moderate-to-severe RA who have had an inadequate response or intolerance to biologic or targeted synthetic DMARDs.

The specific objective of the open-label follow-up with all subjects receiving active stimulation is to gather long-term safety and exploratory efficacy data.

3.2 Study Design

This is an operationally seamless, 2-stage, randomized, sham-controlled, double-blind, multicenter pivotal study enrolling up to 250 randomized subjects at up to 45 study centers across the U.S. After completing a 12-week follow-up for the primary efficacy endpoint, there is a one-way crossover of the control group and a 252-week follow-up of all subjects on active stimulation for long-term safety and exploratory efficacy data. The blinding to the original treatment assignment will be maintained until the last subject completes Week 12 assessments, and the study dataset for the primary analysis is locked.

3.3 Study Visits and Assessments During Extension

The open-label follow-up will begin after completion of assessments at Week 12 and a one-way crossover of the control group to active stimulation. Subjects receiving active stimulation will continue on active stimulation. Subjects will return for 3 device titration visits (Titration 4, 5 and 6 at Week 13, 14, 15, respectively), and 21 follow-up assessment visits every 12 weeks from Week 24 through Week 264 (end of study). See **Appendix A** for Schedule of Assessments.

4 TYPE OF PLANNED ANALYSES

4.1 DMC Analysis

An independent Data Monitoring Committee (DMC) consisting of external, independent rheumatology, surgery and biostatistics experts will continue to provide ongoing monitoring of the safety, efficacy and overall study conduct. The DMC's role and responsibilities and the scope of

study oversight are detailed in the DMC Charter, which defines the DMC membership, meeting logistics, and meeting frequency.

During long-term extension, once the last study subject has been enrolled, the DMC will continue to meet once every 6 months and provide recommendations for continuing or stopping the study based on their ongoing review of cumulative safety data, including AEs, SAEs, device deficiencies, protocol deviations, and concomitant medications, as well as descriptive summaries of TJC28 and SJC28.

The DMC meetings will be performed in closed sessions until the study is unblinded. Data access is described in **Table 1**

Table 1: Data Access Matrix During Open-Label Extension

Department/Role	Blinded	Unblinded	Note
CEO	B		Receiving DMC recommendations
Clinical Operations ¹	B	--	Not having access to randomization assignments or DMC Closed Session reports to preserve blinding of everyone involved directly or indirectly in the study conduct until locking the study dataset for the primary efficacy analysis at Week 12
Clinical Data Management	B	--	Consultants to sponsor responsible for managing EDC and IRT, generating data exports and not having access to randomization assignments until locking the study dataset for the primary efficacy analysis at Week 12
Study Biostatisticians	B	--	Consultants to sponsor responsible for programming but not having access to randomization assignments until locking the study dataset for the primary efficacy analysis at Week 12.
Independent Biostatistician	--	U	Non-voting statistician reporting to DMC responsible for receiving blinded data exports, accessing randomization assignments, conducting unblinded analyses and preparing outputs for review during DMC closed sessions
DMC	--	U	DMC chairperson, biostatistician, and clinicians participating in closed meetings

Abbreviations: B, blinded; CEO, Chief Executive Officer; DMC, data monitoring committee; EDC, electronic data capture; U, unblinded.

¹Clinical operations includes but is not limited to Chief Medical Officer, Vice President of Clinical Affairs, Managers of Clinical Affairs/Operations, Clinical Research Associates, Field Clinical Engineers.

4.2 Exploratory Analysis

During the open-label follow-up, changes in exploratory efficacy endpoints at Week 24, 48, 96, 144 and 264 (end of study) will be evaluated in comparison to baseline and Day 0 for the treatment population and Week 12 for the crossover population using data for all subjects available at a given timepoint (**Table 2**). Refer to Section 5.2 for definitions of populations.

Table 2: Summary of Exploratory Efficacy Endpoints

Endpoint	Display	TOL	COL	Subgroup
ACR20/50/70 response	T, L	Y	Y	Y [1]
DAS28-CRP moderate/good EULAR response	T, L	Y	Y	Y
DAS28-CRP response (MCID)	T, L	Y	Y	Y
HAQ-DI score change and response (MCID)	T, L	Y	Y	Y
ACR components (TJC28, SJC28, Subject Pain, SGA, HAQ-DI, EGA, hsCRP) 20/50/70response	T, L	Y	Y	--
DAS28-CRP score change, LDA/remission	T, L	Y	Y	--
CDAI score change, LDA/remission, response (MCID)	T, L	Y	Y	--
RAMRIS (bone erosion, osteitis, synovitis, CARLOS) score change, progression (bone erosion) at Week 24	T, L	Y	Y	--
EQ-5D-5L score change	T, L	Y	Y	--
SF-36/PCS/MCS score change	T, L	Y	Y	--
Percent change in inflammatory biomarkers at Week 24	T, L	Y	Y	--
Subject satisfaction at Week 24	T, L	Y	Y	--

Abbreviations: ACR, American College of Rheumatology; CARLOS, cartilage loss score; CDAI, Clinical Disease Activity Index; COL, control to open label; CRP, C-reactive protein; DAS, Disease Activity Score; EGA, evaluator's global assessment; EQ-5d-5L, EuroQol 5 domains 5 levels; EULAR, European League Against Rheumatism; HAQ-DI, Health Assessment Questionnaire Disability Index; hsCRP, high sensitivity CRP; L, listings; LDA, low disease activity; RAMRIS, Rheumatoid Arthritis MRI Scoring System; SF-36, Short Form Survey with 36 items; SGA, subject's global assessment; T, tables; TJC, tender joint count; TOL, treatment to open label; SJC, swollen joint count; Y, yes.

[1] Subgroup analyses as defined in Section 6.3

Note: All score values are determined at all timepoints, unless stated otherwise. All response rates are determined based on change from baseline (i.e., on the day of informed consent for OL PTE population and Week 12 for CO PTE population) to a specified timepoint. Refer to Section 5.2 for definitions of populations Sections 6.2 for definition of response for specific endpoints.

5 STATISTICAL METHODS

5.1 General Considerations for Data Analyses

The exploratory analyses and safety evaluations are considered *a priori* analyses because they have been prespecified in the SAP prior to locking the database. All other analyses, if any, designed subsequent to locking the database will be considered *post-hoc* analyses, and their results will be considered exploratory. Any *post hoc* analyses will be clearly identified in the clinical study report.

Continuous data will be summarized in terms of the mean, SD, median, minimum, maximum and number of observations, unless otherwise stated. The minimum and maximum will be reported to the same number of decimal places as the raw data recorded in the database. The mean and median will be reported to 1 more decimal place than the raw data recorded in the database. The SD will be reported to 2 more decimal places than the raw data recorded in the database. In general, the maximum number of decimal places reported shall be 4 for any summary statistic.

Categorical data will be summarized in terms of the number of subjects providing data at the relevant time point, frequency counts and percentages. If not stated otherwise, percentages will be presented with one decimal place. Percentages will not be presented for zero counts. Percentages will be calculated using n as the denominator. 100% will be presented without decimal places.

95% Confidence intervals (CI) will be presented to 1 more decimal place than the raw data. Unless stated otherwise, a two-sided 95% confidence level will be calculated when confidence interval is presented.

Data from the protocol-specified visits (i.e., as reported in CRF) will be used in the summary tables (**Appendix B**) and data listings (**Appendix C**). All report outputs will be produced using a software package widely recognized as acceptable for analyzing clinical data in a secure and validated environment.

5.2 Analysis Populations

Analysis population defines the subjects to be included in an analysis. The exploratory analyses will be conducted on the Treatment to Open Label (TOL) and Control to Open Label (COL) populations. The safety analyses will be evaluated on the safety population. All analysis populations are defined below and the exploratory endpoints summarized in **Table 2**.

- *Treatment to Open Label (TOL)*: The TOL population comprises treatment subjects from ITT population who received active stimulation through Week 12, completed Week 12 assessments, continued to receive active stimulation during open-label follow-up, and for whom follow-up data are available.
- *Control to Open Label (COL)*: The COL population comprises Control subjects from ITT population who received non-active (sham) stimulation through Week 12, switched to active stimulation after completing Week 12 assessments, continued to receive active stimulation during open-label follow-up, and for whom follow-up data are available.
- *Safety population*. All enrolled subjects.

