11.6 Follow-up

The follow-up period begins immediately post-randomization and initiation of stimulation. Each subject will return for 6 follow-up visits between Day 0 and Week 12, and 24 follow-up visits in the open-label, long-term follow-up period, starting after Week 12 assessments and continuing through Week 264 (end of study). Visits must occur within specified windows from Day 0 as detailed in Schedule of Assessments (see Section 6).

The protocol-required follow-up assessments are described in the following sections.

11.6.1 Follow-up through Week 12

The protocol-required follow-up assessments at Week 4, 8 and 12 include the following and should be performed in the order specified prior to the device check and any dose adjustment:

- Subject's, Joint Evaluator's and Co-PI Rheumatologist blinding assessment (Week 4 and 12)
- Collection of vital signs (Week 12)
- 12-lead ECG (Week 12)
- Pregnancy test for female subjects with childbearing potential and confirmation of birth control method (see Section 12.1)
- RA disease activity assessments (see Section 12.2)
- SF-36 and EQ-5D-5L questionnaires
- Blood collection for CBC and inflammatory biomarkers (see Section 12.3)
- Reporting of any AEs, device deficiencies and change in concomitant medications
- Suspending therapy before the hand MRI (Week 12; see Section 11.8)
- Hand MRI (Week 12; see Section 12.4)
- Review of clinical outcomes and discussion of treatment options for continuation in the long-term follow-up period of the study (after completing assessments at Week 12). The Co-PI Rheumatologist will review with the subject their clinical outcomes and determine which option is in the subject's best interest. The Co-PI Rheumatologist and the subject are blinded to initial treatment assignment in making this decision. The option chosen will be recorded on the follow-up visit CRF and entered into EDC. Options include:
 - Receive active stimulation
 - Receive additional RA treatment with active stimulation (see Section 14.5)
 - Receive additional RA treatment without active stimulation (i.e., stimulation is suspended, see Section 11.8) with a possibility to receive active stimulation at a later time
 - Permanently turn off (decommission) the study implant (see Section 11.9)
 - Undergo an explant procedure to surgically remove the implant (see Section 11.10)

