11.8 Suspending and Resuming Stimulation

Stimulation must be suspended before an MRI, prior to an elective surgical procedure, or if there is a concern of subject's safety.

Additionally, stimulation may be suspended at any time after completion of Week 12 assessments at the discretion of the clinical investigator and the subject. The clinical investigator and subject may decide to suspend stimulation in the event the subject experiences worsening of RA symptoms or if the subject does not experience adequate clinical improvement and continuation of stimulation is deemed not in the best interest of the subject (e.g., subject experiences AE that is definitely or probably related to stimulation). RA disease activity is assessed and documented at all follow-up visits. Results from these assessments may be used to guide decision-making.

MicroRegulator should be fully charged prior to suspending stimulation. Stimulation from MicroRegulator can be suspended by Prescription Pad as detailed under "Suspending Therapy" section of the SetPoint System IFU Prescriber Manual. Pink visual indicator on Energizer confirms therapy suspension. Stimulation will no longer be delivered until therapy is resumed. Subjects should continue to follow the regular visit schedule, adhere to all study procedures and be monitored for safety while therapy is suspended.

If the clinical investigator and subject decide to resume stimulation (examples include, but are not limited to, following resolution of AE, after MRI, after elective procedure), stimulation from MicroRegulator can be resumed by Prescription Pad as detailed under "Resuming Therapy" section of the SetPoint System IFU Prescriber Manual. Green or orange visual indicator on Energizer confirms that therapy has been resumed.

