11.9 Implant Decommissioning

Implant battery charge level will be monitored by the designated research coordinator at every follow-up visit. If a charge level of less than 75% is observed, the subject will be counseled on the importance of charging their implant on a weekly basis and be reminded that their implant will be decommissioned in the event the subject does not comply. Once fully discharged, the battery cannot be recharged, and automatic delivery of stimulation will no longer occur. In this case, the MicroRegulator must be decommissioned (permanently turned off) and the subject must return all external equipment (Energizer and Wireless Charger). Contact SetPoint Medical to request placement of the MicroRegulator in decommission mode. If a subject wants or needs to have their implant permanently turned off and left in place at the end of the study or earlier, the implant will be decommissioned in accordance with the SetPoint System Instructions for Use Prescriber Manual. The subject would be required to return their Energizer and visit the site at least 24 hours following the initiation of decommissioning, to ensure that the decommissioning process occurred as expected.

Subjects that have their implant decommissioned prior to Week 264 and remain in the study should continue to follow the regular visit schedule, adhere to all study procedures and be

CONFIDENTIAL

May not be reproduced outside of SetPoint Medical without written permission from Document Control.

62 of 111

monitored for safety. Subjects choosing to end participation after implant decommissioning will be asked to contact the clinical investigator in the event they experience any safety issue related to the investigational implant.

If a device failure precludes decommissioning, the subject will be followed for safety for a period of 10 months, at which point the internal battery would be fully depleted. If the 10-month period has not elapsed at the point the subject exits the study, investigator agrees to follow subject under their standard of care. In this case, follow-up will constitute documented contact with the subject once every 2 months, along with documentation of any reported AEs. Subjects will be informed about the risks associated with attempting to recharge a device that has a completely depleted battery.

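### CLP-008 reports long-term efficacy only in subjects who stayed on stimulation, so the TOL response rate can rise through selection at Week 12

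*SAP*

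**What the plan says.** CLP-008 5.2 fixes the efficacy populations: "The exploratory analyses will be conducted on the Treatment to Open Label (TOL) and Control to Open Label (COL) populations". Both are limited to ITT subjects who "continued to receive active stimulation during open-label follow-up, and for whom follow-up data are available"; COL members must also have switched to active stimulation after Week 12. Protocol 17.8 has the same definitions.

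Protocol 11.6.1 makes staying on stimulation a choice taken at Week 12. The Co-PI Rheumatologist "will review with the subject their clinical outcomes and determine which option" serves the subject best, with both of them blinded to assignment. Two of the five options keep stimulation, one of them with added drug. The other three do not: "Receive additional RA treatment without active stimulation", decommissioning, and explant. Protocol 11.8 allows suspension after Week 12 when RA worsens, or "if the subject does not experience adequate clinical improvement and continuation of stimulation is deemed not in the best interest of the subject". Its example of the latter is an adverse event related to stimulation.

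Follow-up after coming off depends on the route:
- Suspended (11.8): "Subjects should continue to follow the regular visit schedule, adhere to all study procedures and be monitored for safety while therapy is suspended".
- Decommissioned (11.9): "Subjects that have their implant decommissioned prior to Week 264 and remain in the study should continue to follow the regular visit schedule". They may instead end participation.
- Explanted (11.10): the subject leaves the study after surgical clearance.

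In CLP-008, TOL response is counted from informed consent or from Day 0, and COL response from Week 12 (Table 14.8.2.1, footnotes [4] and [5]). The efficacy shells have TOL and COL columns only.

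**The concern.** TOL membership is settled after randomization by a decision taken with the Week 12 outcome in view, while TOL response is still measured from a point before that decision. If poor responders leave stimulation more often than good ones, they drop out of numerator and denominator together and the remaining rate goes up. A reader who knows the Week 12 ITT result and then sees a higher TOL rate at Week 24 or later could take it for durable or growing benefit.

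Nothing else in CLP-008 brings these subjects back. The augmented-therapy subgroup (6.3) covers subjects who combine stimulation with added drug. Non-responder imputation is listed in 6.1.1 as a method that may be used, but it cannot act on subjects outside the population. The loss is also hard to see: disposition Table 14.8.1.1 starts from TOL and COL, Listing 16.8.2.1 holds only their members, and Listing 16.8.2.3 gives no reason for exclusion, although CLP-004 Listing 16.1.2.3 does so for the PTE population.

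**Working it through.** **Inputs**
- Treatment-group ACR20 response at Week 12: 60% in the design case, 50% in the lower case (Protocol 17.2; CLP-004 3.4).
- Group size: 240/2 = 120, the minimum enrolment with 1:1 allocation.
- Share coming off stimulation at Week 12: not in the documents, so assumed.

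**Design figure.** A simulation of 1,000,000 trials (30 per arm at Stage 1, stop if the observed difference is below 10%, then 125 per arm, pooled chi-square test) gives power 0.9585 and stopping probability 0.040 for 60% against 30%. The plan states 0.959 and 0.040. This confirms only how the design inputs are read; the point disputes no stated number.

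**Selection effect.** Let R be the Week 12 responders among N subjects, and let k non-responders leave stimulation. If nobody's status changes afterwards, the TOL rate is R/(N − k).

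| Week 12 rate | k = 0 | k = 6 (5%) | k = 12 (10%) |
|---|---|---|---|
| 60% (R = 72) | 72/120 = 60.0% | 72/114 = 63.2% | 72/108 = 66.7% |
| 50% (R = 60) | 60/120 = 50.0% | 60/114 = 52.6% | 60/108 = 55.6% |

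Here every leaver is a non-responder, which is the upper end for a given number of leavers.

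**When responders leave too.** If a share g of responders and a share f of non-responders come off, the rate is R(1 − g) / [R(1 − g) + (N − R)(1 − f)]. With N = 120, R = 72 and N − R = 48:
- f = 20%, g = 0: 72/(72 + 38.4) = 65.2%
- f = 20%, g = 10%: 64.8/(64.8 + 38.4) = 62.8%
- f = g = 10%: 64.8/(64.8 + 43.2) = 60.0%, no shift
- f = 0, g = 10%: 64.8/(64.8 + 48) = 57.4%, a fall

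The rate rises only when f exceeds g.

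**Reach.** The efficacy shells run every 12 weeks from Week 24 to Week 192: (192 − 24)/12 + 1 = 15 visits. A Week 12 exclusion carries through all of them. For COL the reference is Week 12 itself, so the direction of the effect cannot be derived.

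**Denominator.** CLP-008 5.1 takes percentages over n, the subjects providing data, and 5.5 leaves missing data and withdrawals missing. Table 14.8.2.1 footnote [3] takes percentages over the analysis population, under which a missing subject in TOL counts as a non-response. These rules give different rates whenever a TOL subject misses a visit.

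**The case against.** The strongest reply is that the mechanism may be weak. A non-responder can add drug and stay on stimulation, and neither party knows whether that subject had sham. In SPM-011, 8 of the 11 subjects still enrolled at 24 months had added a biologic or targeted synthetic DMARD (Protocol 7.3.2), which suggests that poor responders may augment and stay. A reader might infer that lack of response alone leads to suspension; 11.8 also requires that continuing is not in the subject's interest, and its example is an adverse event, which need not fall on non-responders. This stands, and it is why only a conditional rise can be claimed.

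Other tempting readings also go too far:
- That everyone who comes off is still followed. Explanted subjects exit, and decommissioned subjects may leave.
- That any later suspension or explant removes a subject from TOL. The shells suggest otherwise: Table 14.8.2.20 has suspended and explanted rows under TOL and COL, and Listings 16.8.2.6.1 and 16.8.2.6.2 record explant and suspension by those populations. Nor do the documents say whether someone suspended at Week 12 who later resumes enters TOL.
- That about a fifth of subjects would come off at Week 12, from 3 of 14 (21%) in SPM-011 and 4 of 18 (22%) in SPM-006. Those are study exits over 2 to 4 years, not stimulation choices at Week 12.
- That the plan itself compares the Week 12 ITT rate with later TOL rates. CLP-008 tabulates from Week 24, gives confidence intervals without tests, and defines TOL and COL in footnotes.

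It can also be said that the open-label period is mainly for safety, which is analysed in all enrolled subjects. That limits the importance of the point. It does not remove it: exploratory efficacy is a stated aim of the period (CLP-008 3.1), and the definition excludes a subject who is off stimulation from Week 12 onward.

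**Conclusion.** The point holds as a minor one. A treatment-arm subject who comes off stimulation at Week 12 and stays off is outside TOL, and no CLP-008 efficacy row includes that subject, even where the visits are attended. If non-responders come off more often than responders, TOL response rises by selection alone: with 120 subjects, by 3.2 or 6.7 points at a 60% rate, or 2.6 or 5.6 points at 50%, for 6 or 12 leavers. These sizes rest on assumed leaver numbers with every leaver a non-responder; the shift is zero at equal leaving rates and reverses if responders leave more often. The denominator conflict is a separate ambiguity within the same tables.

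A reader might infer that the Week 12 evidence is touched. It is not: the primary and key secondary analyses are in CLP-004 on the ITT population, which includes these subjects, and the safety tables cover all enrolled subjects.

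**What to change.** Keep TOL and COL as on-stimulation summaries. Beside them, for ACR20/50/70, EULAR response, DAS28-CRP MCID and HAQ-DI MCID, add supplementary rows for all ITT subjects by original group:
- (a) observed response whatever the stimulation status;
- (b) subjects off stimulation or withdrawn counted as non-responders.

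State one denominator and use it in 5.1 and in the table footnotes. Add to Table 14.8.1.1 the flow from ITT through the option chosen at Week 12 to TOL and COL, and add an exclusion-reason column to Listing 16.8.2.3. COL needs no new wording, because it already requires the switch to active stimulation.

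The cost is a short SAP revision and programming, with no new data collection: "The option chosen will be recorded on the follow-up visit CRF and entered into EDC", and subjects off stimulation who remain in the study attend the visits. The revision should precede database lock, since 5.1 classes anything designed later as post hoc. The downside is interpretive. Row set (a) includes the effect of other RA drugs, and row set (b) will usually be lower than the TOL rate, so both should be labelled as supplementary.
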